 7.6 FUNDING10

 7.7 AUDITS10

8. STUDY MANAGEMENT10

9. PUBLICATION POLICY.....10

STUDY SUMMARY

TITLE

Genomic Imaging in Neonatal Encephalopathy

DESIGN

Prospective observational multicentre cohort study

BACKGROUND

Half of the babies receiving cooling therapy for neonatal encephalopathy still have adverse outcomes. Therefore, for the development of personalised neuroprotective therapies it is essential that we are able to rapidly identify those babies who will not respond to cooling, and understand why they do not respond. In this work, we will examine the feasibility of three different genetic classifying methods (host gene expression profile, epigenetics, and copy number variants) for disease stratification in babies with neonatal encephalopathy.

AIMS

1. To compare the host gene expression with brain injury at birth, and neurodisability at two years of age in babies after neonatal encephalopathy
2. To examine the relation of epigenetic changes with brain injury at birth, and neurodisability at two years of age in babies after neonatal encephalopathy
3. To examine the association of copy number variants with brain injury at birth, and neurodisability at two years of age in babies after neonatal encephalopathy

METHODS

A total of 300 term encephalopathic babies will be recruited from participating NHS hospitals over a 3 year period. A small amount of blood will be collected soon after birth and will be sent to Imperial College London for genomic analysis. We will also collect blood from the parents of the recruited babies to examine the concordance in their copy number variants. All babies will have magnetic resonance scans performed during the neonatal period and detailed neurodevelopmental assessment between 18 to 24 months, as a part of their routine clinical care.

DATA ANALYSIS AND OUTCOME MEASURES

Next generation sequencing and bioinformatic analysis will be used to identify a minimal set of activated or deactivated genes ('gene signature') that is associated with brain injury patterns and long-term disability.

POPULATION

300 newborn babies with hypoxic ischaemic encephalopathy
600 parents of the recruited babies with hypoxic ischemic encephalopathy.

DURATION

3 year recruitment followed by a neurodevelopmental assessment between 18 to 24 months after birth.

BENEFITS

Our goal is to develop a point-of-care test for disease stratification in neonatal encephalopathy. If successful, this will lead to a paradigm shift in the way we identify and treat babies with this condition, and will open up many new opportunities for the development of individualised neuroprotective therapies.

1. INTRODUCTION

1.1 BACKGROUND

Need for a rapid diagnostic test at birth in neonatal encephalopathy

Neonatal encephalopathy (NE) is presumed to be the end point of an acute and unexpected reduction in blood flow and oxygen to the fetal brain, immediately prior to delivery. A few hours after birth the injury progresses to catastrophic secondary energy failure, leading to permanent brain damage. Therefore, it is vitally important to identify babies at risk of long-term neurodisability as early as possible after birth, to initiate preventative therapy. Without appropriate treatment approximately one third of affected babies die, and up to two thirds develop long-term neurodisability, with a cost to the NHS of £750,000 for each affected child.¹

In recent years, therapeutic hypothermia (cooling initiated within 6 hours of birth and continued for 3 days) has been adopted in the NHS as the first effective therapy for neonatal encephalopathy. This therapy reduces the likelihood of death (Risk Ratio (RR) 0.75; 95% Confidence Intervals (CI) 0.64 to 0.88), and neurodisability (RR 0.77; 95% CI 0.63 to 0.94) after moderate or severe neonatal encephalopathy, and has led to a substantial reduction in mortality and morbidity, saving the NHS approximately £125 million per year.²

Despite cooling, approximately half of these babies still develop adverse outcomes. Although many adjunct neuroprotective therapies have proven efficacy in preclinical models of 'pure hypoxic ischemic injury', clinical translation is challenging due to the heterogeneity of neonatal encephalopathy. In fact, only one third can be attributed to an acute intrapartum hypoxic insult, whilst subacute injury from perinatal infection and inflammation may be responsible for the vast majority.

The successful development of personalised neuroprotection therapies in encephalopathy (for example, in the case of sub-acute brain injury, infection, inflammation or an acute intrapartum event) requires a robust point-of-care test for disease stratification which is based on aetiology, and targeted monitoring of therapeutic pathways. However, although advanced magnetic resonance (MR) biomarkers (whole brain fractional anisotropy, neurite orientation dispersion and density imaging, spectroscopy) are useful in disease stratification, performing MR scans soon after birth is not realistic (i.e. within the therapeutic window period for effective neuroprotection).

Therefore, there is now a concerted effort from the research community to develop *an effective test at birth to identify babies at the highest risk of long-term neurodisability* who can be candidates for additional therapeutic strategies.

Magnetic resonance imaging patterns in neonatal encephalopathy

Magnetic resonance imaging can effectively stratify neonatal encephalopathy based on aetiology. Preclinical and clinical evidence suggest that different MRI patterns of brain injury reflect different aetiologies in neonatal encephalopathy.³ Sub-acute and chronic hypoxic insults produce a parasagittal watershed zone of infarcts (white matter injury) whereas an acute hypoxic ischaemic event results in injury to the most metabolically active tissues such as the basal ganglia and thalami (BGT), as well as the corticospinal tracts.

Grey matter neurons and early myelinating tissues have a higher metabolic rate than the surrounding white matter. Hence, they are significantly more vulnerable to acute anoxia than the hemispheric white matter, although the duration of ischaemia resulting from a sentinel event may be relatively short. The different MRI injury patterns are related to different outcomes.^{3,4} Loss of the normal signal intensity from the motor corticospinal tract is strongly associated with adjacent BGT injury and acts as reliable predictor of abnormal motor outcomes. On the other hand, white matter injury is mainly associated with cognitive function and language development at school age.⁵

Biomarkers for early identification of 'at-risk' encephalopathic infants

The full clinical picture of encephalopathy evolves over the first few days after birth. Hence, clinical examination at birth alone cannot identify all babies at risk of adverse outcome (area under the curve 0.65).⁶ Although a number of serum biomarkers have been extensively studied for many years, none have

Genomic Imaging in Neonatal Encephalopathy

sufficient accuracy to influence treatment decisions.⁷ Early amplitude integrated electroencephalography (aEEG) has a low positive predictive value (60%), which drops even further in cooled infants.⁸ Although MR biomarkers are the most accurate predictors of long-term adverse outcomes after neonatal encephalopathy – particularly the lactate:N-acetylaspartate metabolite peak area ratio (Lac/NAA) derived from proton MR spectroscopy (¹H MRS) – performing MR scans within few hours after birth is unrealistic.⁹ Thus, there is an unmet need for a rapid or point-of-care test for the identification and disease stratification of encephalopathic babies at risk of adverse neurological outcomes, soon after birth.

2. METHODS FOR DISEASE STRATIFICATION

2.1 Gene expression in neonatal encephalopathy

Gene expression profiling (transcriptomics) provides a snapshot of the biological processes that occur in response to internal or external stimuli. Changes in gene activity (expression) occur rapidly, and patterns of increased or decreased transcript abundance can provide both a route map of cellular pathological processes, and a ‘signature’ used for diagnostic or prognostic classification. Genome wide expression profiling is well established in cancer research for predicting clinical outcome, identifying the presence of metastases, and developing personalised treatment.¹⁰ More recently, specific expression patterns and pathways have been described in several serious infections, including paediatric tuberculosis, allowing disease stratification.^{11,12} This is currently being developed as a rapid point-of-care test.

Although gene expression profiling has not yet been reported in babies with neonatal encephalopathy, preclinical data (animal models) suggest up-regulation of genes involved in neurogenesis and autophagy.¹³ Furthermore, an overall decrease of endocytotic capacity has been found during hypoxia, suggesting an oxygen-dependent uptake of different macromolecular ligands, or a hypoxia induced paralysis.¹⁴

2.2 Epigenetics in neonatal encephalopathy

There is growing evidence indicating that epigenetic modification of gene expression, such as DNA methylation or histone modifications, may be one important mechanism underlying the “developmental origins of adult disease”.¹⁵ As a heritable epigenetic marker, DNA methylation is the most widely studied epigenetic phenomenon. The aberrant DNA methylation of promoters leads to abnormalities in gene transcription, which ultimately influence gene expression. Much of the epigenome is established during embryogenesis and early development of the fetus. DNA methylation mediates the growth and maintenance of tissue-specific expression profiles in different cell types and plays an essential role in organogenesis and fetal development.¹⁵

The brain is the central organ responsible for stress responses, and undergoes parallel alterations in its structure and function in response to stress events.¹⁶ There is increasing evidence suggesting that epigenetic machinery orchestrates the development, plasticity, homeostasis and evolutionary innovations of the brain. Recent studies suggest that epigenetic programming in response to fetal hypoxia is responsible for the development of a hypoxic–ischemia sensitive phenotype in the brain, implicating a key role of epigenetic modifications in fetal stress-mediated neuronal and vascular dysfunctions.^{17,18}

2.3 Genetic contribution to neonatal encephalopathy

At least a proportion of the encephalopathic babies who develop cerebral palsy can be explained by complex genetics.¹⁹ Copy number variants (CNVs), which are rare (<1%) genetic deletions and duplications, may predispose to cerebral palsy (CP) by interacting with environmental triggers. Predisposing variants are likely to be oligogenic or polygenic and thus additive in nature and require gene-environment investigations. Such variants would increase the risk of a CP phenotype, and not deterministic of CP. Established environmental risk factors for CP, such as IUGR and infection, may interact with predisposing genetic variants and potentiate the chance of a CP outcome.

A recent pilot study has found that ten out of 50 singleton CP cases had potentially relevant CNVs. However all of these were inherited from a healthy parent, suggesting another genetic or environmental contributing factor.²⁰ Such an inheritance pattern is usual for other neurodevelopmental disorders such as intellectual disability or autism.

Genomic Imaging in Neonatal Encephalopathy

In another study from Israel, 16 CP cases out of 52 cases (31%) of unknown aetiology had CNVs that were likely to be pathogenic, and 12 of these were de novo.²¹ Currently, the combination of 14% of cases with likely pathogenic point mutations and 20-31% with CNVs of interest gives a potential genetic contribution to causation in up to 34-45% of CP cases.²²

3. STUDY AIMS

Primary

1. To compare the activity of specific genes in blood (host gene expression) at birth with brain injury on magnetic resonance scans within two weeks of birth, and with neurodisability at two years of age in babies with neonatal encephalopathy

Secondary

1. To identify and characterise the host gene expression pathways associated with basal ganglia/thalamic injury and white matter injury on magnetic resonance scans in neonatal encephalopathy
2. To identify a minimal transcriptomic signature of adverse neurological outcomes
3. To examine the relation of epigenetic changes with brain injury and neurodisability after neonatal encephalopathy
4. To examine the association of copy number variants with brain injury and neurodisability after neonatal encephalopathy

4. PATIENTS AND METHODS

4.1 Study design and sites

The GENIE Study is a prospective observational multicentre cohort study. It is open for all tertiary neonatal units offering cooling therapy to babies with neonatal encephalopathy. The recruiting centres should be offering magnetic resonance scans and neurodevelopmental outcome assessment between 18 to 24 months, as a part of standard clinical care.

4.2 Study participants

We will recruit a total of 300 term or near term (>35 weeks) babies with neonatal encephalopathy over a 3 year period.

4.3 Inclusion criteria

All babies with clinical evidence of encephalopathy (mild, moderate or severe) within 6 hours of birth, along with evidence of an intra-partum asphyxial insult. Whilst most babies may also receive cooling therapy, babies who are not receiving this are also eligible.

Both parents of the encephalopathic babies will be also recruited into the study, and their blood will be collected for testing of copy number variants.

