5. STATISTICS AND DATA ANALYSIS

Statistical analysis will be performed using R (version 3.3.2). In order to identify lists of differentially expressed transcripts between the patient groups for biological interpretation, we will fit linear regression models and calculate moderated t statistics for each transcript. The p values will be corrected for multiple testing using the Benjamini-Hochberg false discovery rate method to control for type I errors. We will use computational network-based approaches to unravel the underlying biological processes, which produce the gene expression measurements. IPA (<http://www.ingenuity.com>), DAVID, and a manually curated data set of human gene interactions in InnateDB (<http://www.innatedb.com>) will be used to examine biological network relationships and any associations with known pathways. To identify signatures of differentially expressed transcripts with diagnostic potential, we will apply variable selection methods to the significantly differentially expressed transcripts using the disease risk score, and its predictive accuracy will be calculated using the pROC package in R. The area under the receiver operating characteristic curve, sensitivity, and specificity will be assessed.

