5.1 Sample size calculation

A total sample size of 272 patients (R (v3.3.1) and RNASeqPower (v1.12.0): 108 babies with WM injury, 82 with BGT injury, 82 with normal MR scans and 136 babies with adverse outcome) is required, based on the following assumptions supported by our preliminary data:

(i) RNA-sequencing depth of at least 30 million of reads (ii) Variance of 1.01 between encephalopathic babies with adverse outcomes and those with a normal outcome (iii) Variance of 0.9 between encephalopathic babies with normal MR scans and those with WM injury, and 0.78 between encephalopathic babies with normal MR scans and those with basal ganglia injury (iv) Type I error rate of 0.05 and Type II error rate of 0.1 (90% power). Our preliminary data suggest WM injury in 40%, basal ganglia injury in 30 %, normal MR scans in 30%, and a 50% with an adverse outcome.

Genomic Imaging in Neonatal Encephalopathy

We have increased the total sample size to 300 to accommodate a 10% drop-out rate, and poor MR data quality.

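### Section 5 assesses the signature's accuracy over a mild-to-severe cohort without reference to clinical grade, so a good AUC may partly reflect grade and would not show that the blood test adds to examination at birth

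*Protocol*

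**What the plan says.** Section 4.3 of the protocol admits every grade: "All babies with clinical evidence of encephalopathy (mild, moderate or severe) within 6 hours of birth". It sets no quota by grade. It also says: "Whilst most babies may also receive cooling therapy, babies who are not receiving this are also eligible". Section 4.6 has the baby's blood drawn within 6 hours of birth, the same window as the clinical assessment for entry.

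Section 5 derives a risk score from the differentially expressed transcripts and evaluates it with the pROC package: "The area under the receiver operating characteristic curve, sensitivity, and specificity will be assessed". It names no clinical comparator and no restriction or stratification by grade.

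Section 1.1 supplies the rationale. It credits clinical examination at birth with an AUC of 0.65 and presents this as a reason to look for a better test. Section 7.2 says that the study is meant to inform treatment decisions within 6 hours of birth.

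**The concern.** A test at birth would be used by a clinician who has already examined the baby. The useful question is whether the blood result improves on that examination. An AUC pooled over mild, moderate and severe babies answers a different question, namely whether the score separates adverse from normal outcomes in the whole cohort.

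The two answers can differ widely. Suppose the signature carries information about outcome only because it follows grade. Mild babies, most of whom would be expected to do well, then receive low scores and are classified correctly, which raises the AUC. The result looks like a useful test, yet it tells the clinician nothing new.

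Comparing the pooled AUC with the 0.65 in section 1.1 does not settle this. That figure comes from a cited study whose grade mix the protocol does not give, and an AUC depends on the mix of babies in which it is measured.

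**Working it through.** **Inputs from the protocol.** All grades are eligible (section 4.3). About half of cooled babies have an adverse outcome, in a paragraph that follows one on moderate or severe encephalopathy (section 1.1). Clinical examination has an AUC of 0.65 (section 1.1). Section 5.1 plans 272 evaluable babies, 136 of them adverse, which reproduces as 0.50 × 272 = 136.

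**Inputs assumed.** The share of each grade and the adverse risk by grade are not in the protocol. Two mixes are used, written as mild/moderate/severe:

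- Mix A: shares 30/50/20%, adverse risks 10/40/80%.
- Mix B: shares 20/60/20%, adverse risks 15/45/65%.

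Both keep the moderate and severe babies close to one half adverse. A: (0.20 + 0.16)/0.70 = 51%. B: (0.27 + 0.13)/0.80 = 50%.

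**Formula.** AUC of grade alone = sum over grades g of P(g | adverse) × [P(lower grade | normal) + ½ P(g | normal)].

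**Mix A, all babies.** Overall adverse rate 0.03 + 0.20 + 0.16 = 0.39.

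- Adverse babies by grade: 0.077, 0.513, 0.410.
- Normal babies by grade: 0.27, 0.30, 0.04 divided by 0.61 = 0.443, 0.492, 0.066.
- AUC = 0.077 × 0.221 + 0.513 × 0.689 + 0.410 × 0.967 = **0.767**.

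**Mix A, moderate and severe only.** Adverse 0.556, 0.444; normal 0.882, 0.118. AUC = 0.556 × 0.441 + 0.444 × 0.941 = **0.663**.

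**Mix B, all babies.** Overall adverse rate 0.03 + 0.27 + 0.13 = 0.43.

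- Adverse: 0.070, 0.628, 0.302.
- Normal: 0.298, 0.579, 0.123.
- AUC = 0.070 × 0.149 + 0.628 × 0.588 + 0.302 × 0.939 = **0.663**.

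**Mix B, moderate and severe only.** Adverse 0.675, 0.325; normal 0.825, 0.175. AUC = 0.675 × 0.4125 + 0.325 × 0.9125 = **0.575**.

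Including mild babies raises the AUC of grade alone by 0.767 − 0.663 = 0.10 in mix A and by 0.663 − 0.575 = 0.09 in mix B.

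**Cruder check, mild against all others.** Let a share m be mild with adverse risk r, and let the rest have 50% risk. The overall rate is p = 0.5(1 − m) + m·r, and AUC = ½[0.5(1 − m)/p + m(1 − r)/(1 − p)]. With m = 20% and r = 10%, p = 0.42 and AUC = ½(0.952 + 0.310) = 0.63. For m of 10 to 30% and r of 5 to 20%, the AUC is 0.55 to 0.70.

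**Effect on the planned comparison.** Take the stated 90% power at 136 against 136 as given. Power with n₁ adverse and n₂ normal babies is Φ[δ/√(1/n₁ + 1/n₂) − 1.96], where δ = (1.96 + 1.28) × √(2/136), two-sided 5% assumed.

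- 20% mild at 10% risk: 114 adverse of 272, power 89%.
- 30% mild at 10% risk: 103 adverse, power 88%.
- 40% mild at 5% risk: 87 adverse, power 86%.

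**The case against.** The strongest objection is that nothing in the design prevents the better analysis. Clinical data are collected, and a subgroup AUC or a paired comparison is the kind of detail that an SAP may contain. The signature is a secondary aim, the summary calls the work a feasibility study, and section 1.1 sets no formal benchmark to beat. Enrolling all grades is also a legitimate spectrum for a test at birth. All of this is fair, and the point is not that an analysis is missing or that eligibility is wrong. It is that section 5 does state how accuracy will be judged, and that method alone cannot answer the question that section 1.1 raises.

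A second objection is that the illustration is assumed throughout. That stands for the size: the two mixes give 0.77 and 0.66. It does not change the direction, provided mild babies have the lower risk.

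Third, section 1.1 notes that the clinical picture evolves over the first days, so grade at 6 hours is imperfect. That is a reason to measure how much the blood test adds to it.

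A reader might also infer that the adverse cases are over-planned, because section 5.1 assumes "and a 50% with an adverse outcome" and section 1.1 says "Despite cooling, approximately half of these babies still develop adverse outcomes" after describing benefit "after moderate or severe neonatal encephalopathy". The documents do not establish this. Section 5.1 attributes its 50% to preliminary data of unstated grade and cooling mix, which may already include mild babies, and the Study Summary gives the same half for cooled babies without naming a grade.

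Nor does admitting uncooled babies by itself lower the adverse rate. With the risk ratio of 0.77 for neurodisability in section 1.1, uncooled moderate or severe babies would be at higher risk, about 0.50/0.77 = 65%.

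**Conclusion.** The concern holds for the accuracy analysis. Section 5 pools all grades, and a pooled AUC cannot separate the signature's own information from information that the examination already gives. Under the two assumed mixes, grade alone reaches 0.66 to 0.77, at or above the protocol's 0.65 for clinical examination. A signature AUC in that range would not show that the blood test adds anything. The figures rest on grade shares and risks that the protocol does not give.

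The wording must stay conditional. The AUC may partly reflect grade; it would do so only if the transcripts track severity, which is not known. Contrasting moderate with severe babies raises the same issue, so mild babies enlarge the problem but do not create it.

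The point does not extend to the sample size. Even if mild babies did lower the adverse rate, the loss in the scenarios worked above is 1 to 4 points of power.

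**What to change.** In section 5, keep the pooled AUC, sensitivity and specificity, and add two results for adverse outcome:

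1. The AUC of clinical grade alone and of grade plus risk score, in the same babies, with the paired difference and its confidence interval. pROC, already named in section 5, does this.
2. The signature's AUC within moderate and severe babies.

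Name the grade assessed within 6 hours of birth as a recorded variable, since section 4.6 covers it only under routine clinical data. Whatever protects the pooled AUC from overfitting should apply to these results too; otherwise the gain over grade will be flattered.

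The cost is a few sentences and a minor extra analysis, with no additional babies or blood. The gain attributed to the signature may look smaller than the pooled AUC suggests. The subgroup estimate will be less precise: with 70 to 80% moderate or severe, as in the two mixes, about 190 to 218 of the 272 babies contribute.
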